1.0 OVERVIEW OF STUDY DESIGN

This is a two-arm, multi-center United States (U.S.)-based study with a prospective, non-blinded intervention arm (PrismRA arm) and an observational external control arm designed to demonstrate the clinical utility of the PrismRA test in routine clinical care. The study will compare outcomes for rheumatoid arthritis (RA) patients with moderate to high disease activity whose treatment is informed by PrismRA test results (PrismRA arm) to outcomes among RA patients who receive the standard of care (SOC) not informed by PrismRA results (external control arm). The study will be conducted using a modified intention-to-treat (ITT) principle.^[1] All eligible participants meeting inclusion and exclusion criteria *and* initiating the study treatment will be included.

PrismRA arm:

In this arm, all patients will be enrolled into the PrismRA informed treatment selection arm. The Investigator will receive the PrismRA results and use those results to inform treatment selection by Visit 2. Patients may be followed indefinitely from the time of signing the informed consent and medical records release form unless the patient withdraws from the study, dies, or becomes lost to follow-up. Changes to the study biologic and targeted small molecule synthetic disease modifying anti-rheumatic drugs (b/tsDMARDs) do not terminate follow-up following protocol. A patient can withdraw from the study at any time.

External control arm:

The observational external control arm will consist of comparable initiators of b/tsDMARDs in OM1's PremiOM RA dataset, in which the specific choice of tumor necrosis factor inhibitor (TNFi) or non-TNFi b/tsDMARDs was based on the treating physician's clinical judgement and was not informed by the PrismRA test results. Baseline as well as follow-up data will consist of data obtained at routine clinical encounters. The index date (start of follow-up) for this external control arm will be defined as the time of initiation of the study treatment (very first or subsequent b/tsDMARDs) and patients will be followed until week 24, death, or loss to follow-up, whichever occurs first. Changes to the study b/tsDMARDs do not terminate follow-up following protocol. Controls may be sampled from time intervals contemporaneous with the trial (March 2022 and onward) as well as historical periods.

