3.0 STUDY OUTCOMES

In main analyses, binary outcomes measures specified at 12 weeks and 24 weeks below under the Composite Strategy in the ICH E9's estimand framework will be assessed.^[2 3] In the Composite Strategy, a successful outcome will be defined as success achieved at 12 or 24 weeks

and study completed without post-baseline treatment switch during 12 or 24 weeks. In the additional analyses, outcome measures specified at 12 weeks and 24 weeks below will be assessed under the Treatment Policy Strategy. In the Treatment Policy Strategy, any post-baseline treatment switch in the study medication is disregarded.

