3.1 Primary Outcome Measure

The proportion of patients with moderate or high disease activity at baseline who achieve a minimal important difference (MID)[4] in CDAI of ≥ 6 (baseline moderate) or ≥ 12 (baseline high) at 24 weeks after study treatment initiation.

The main Composite Strategy analysis examines the proportion of patients with moderate or high disease activity at baseline who achieve a MID[4] in CDAI of ≥ 6 (baseline moderate) or ≥ 12 (baseline high) at 24 weeks after study treatment initiation AND complete study without post-baseline treatment switch. In the additional Treatment Policy Strategy, continuing the study treatment at 24 weeks is not required.

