6.3.2 Sensitivity Analysis

Sensitivity analyses will assess the robustness of treatment effect estimates to limiting primary endpoint to patients who have the complete CDAI scores.

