Study endpoint	PrismRA	Control	Odds ratio (95% CI)
CDAI MID at 24 weeks	n/N (%)	n/N (%)	x.xx (x.xx-x.xx)
CDAI MID at 12 weeks	n/N (%)	n/N (%)	x.xx (x.xx-x.xx)
CDAI LDA or Remission at 24 weeks	n/N (%)	n/N (%)	x.xx (x.xx-x.xx)
CDAI LDA or Remission at 12 weeks	n/N (%)	n/N (%)	x.xx (x.xx-x.xx)
PtGA MCID at 24 weeks	n/N (%)	n/N (%)	x.xx (x.xx-x.xx)
PtGA MCID at 12 weeks	n/N (%)	n/N (%)	x.xx (x.xx-x.xx)
RAPID3 MCID at 24 weeks	n/N (%)	n/N (%)	x.xx (x.xx-x.xx)
RAPID3 MCID at 12 weeks	n/N (%)	n/N (%)	x.xx (x.xx-x.xx)
Pain VAS MCID at 24 weeks	n/N (%)	n/N (%)	x.xx (x.xx-x.xx)
Pain VAS MCID at 12 weeks	n/N (%)	n/N (%)	x.xx (x.xx-x.xx)
ACR50 at 24 weeks	n/N (%)	n/N (%)	x.xx (x.xx-x.xx)
ACR50 at 12 weeks	n/N (%)	n/N (%)	x.xx (x.xx-x.xx)

Programmer note: N= number of patients with moderate or high disease activity; n= number of patients achieving endpoint criteria

The following Tables will be created using the same layout as Table 2.1.

Table 2.1.1 Primary and secondary composite strategy study endpoints for modified ITT cohort by study arm for TNFi-naïve group

Table 2.1.2 Primary and secondary composite strategy study endpoints for modified ITT cohort by study arm for TNFi-exposed group

Table 2.2 Primary and secondary treatment policy strategy study endpoints for modified ITT cohort by study arm

Table 2.2.1 Primary and secondary treatment policy strategy study endpoints for modified ITT cohort by study arm for TNFi-naïve group

Table 2.2.2 Primary and secondary treatment policy strategy study endpoints for modified ITT cohort by study arm for TNFi-exposed group

Table 2.3 Primary and secondary composite strategy study endpoints for PrismRA-adherent cohort by study arm

Table 2.4 Primary and secondary treatment policy strategy study endpoints for PrismRA-adherent cohort by study arm

Table 3.1 CDAI change from baseline at 12 and 24 weeks for modified ITT cohort by study arm

Characteristic		PrismRA N = xxx	Control N = xxx	Average difference (95% CI)
CDAI at baseline	n	xxx	xxx	
	Mean (s.d.)	xxx (xx.x)	xxx (xx.x)	xxx (xxx-xxx)
	Median (Q1-Q3)	xxx (xxx-xxx)	xxx (xxx-xxx)	
CDAI at 12 weeks	n	xxx	xxx	
	Mean (s.d.)	xxx (xx.x)	xxx (xx.x)	xxx (xxx-xxx)
	Median (Q1-Q3)	xxx (xxx-xxx)	xxx (xxx-xxx)	
Change in CDAI at 12 weeks	n	xxx	xxx	
	Mean (s.d.)	xxx (xx.x)	xxx (xx.x)	xxx (xxx-xxx)
	Median (Q1-Q3)	xxx (xxx-xxx)	xxx (xxx-xxx)	
CDAI at 24 weeks	n	xxx	xxx	
	Mean (s.d.)	xxx (xx.x)	xxx (xx.x)	xxx (xxx-xxx)
	Median (Q1-Q3)	xxx (xxx-xxx)	xxx (xxx-xxx)	

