Change in CDAI at 24 weeks	n	xxx	xxx	
	Mean (s.d.)	xxx (xx.x)	xxx (xx.x)	xxx (xxx-xxx)
	Median (Q1-Q3)	xxx (xxx-xxx)	xxx (xxx-xxx)	

The following Tables will be created using the same layout as Table 3.1.

Table 3.1.1 CDAI change from baseline at 12 and 24 weeks for modified ITT cohort by study arm for TNFi-naïve group

Table 3.1.2 CDAI change from baseline at 12 and 24 weeks for modified ITT cohort by study arm for TNFi- exposed group

Table 3.2 CDAI change from baseline at 12 and 24 weeks for PrismRA-adherent cohort by study arm

The following Table will be created using the same layout as Table 2.1.

Table 4 Sensitivity analyses of primary and secondary composite strategy study endpoints for modified ITT cohort by study arm

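### The complete-CDAI sensitivity analysis drops documented switchers who are failures by definition under the composite endpoint, so it does not isolate the missing-data assumption

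*SAP*

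**What the plan says.** SAP 3.0 makes the Composite Strategy the main analysis for binary outcomes. Success requires "study completed without post-baseline treatment switch during 12 or 24 weeks". For the primary outcome, SAP 3.1 asks for the CDAI improvement "at 24 weeks after study treatment initiation AND complete study without post-baseline treatment switch". SAP 3.2 extends the no-switch condition to the binary secondary endpoints. Under the additional Treatment Policy Strategy, switches are ignored.

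A switch does not take a patient out of the study. SAP 1.0 states: "Changes to the study b/tsDMARDs do not terminate follow-up following protocol."

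The main analysis keeps every eligible initiator and handles missing scores by multiple imputation, deriving the binary endpoints from the imputed scores (SAP 5.4). The sensitivity analysis in SAP 6.3.2 reads: "Sensitivity analyses will assess the robustness of treatment effect estimates to limiting primary endpoint to patients who have the complete CDAI scores." SAP 6.4.2 repeats this for the secondary section. The output shell in SAP 10.0 is titled "Table 4 Sensitivity analyses of primary and secondary composite strategy study endpoints for modified ITT cohort by study arm". It borrows the Table 2.1 layout, and no Treatment Policy counterpart is listed. Nothing in either document says what happens in this analysis to a switcher without a CDAI.

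**The concern.** For the composite endpoint, a missing CDAI and a missing outcome are different things. A documented switcher without a Week 24 CDAI has an observed composite outcome, namely failure. Only a non-switcher without a CDAI has an unknown one. A complete-CDAI filter treats both alike and removes both.

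The check thus changes two things at once: it replaces multiple imputation, and it discards observed failures. If Table 4 differs from Table 2.1, the reader cannot tell which change caused it, and agreement could be accidental. This matters because the SAP expects about half the Week 24 scores to be missing. The alternatives in SAP 8.0 (censoring weights and a tipping-point analysis) are optional, so this is the only committed sensitivity analysis for missing data.

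**Working it through.** **Inputs from the SAP (5.1).** 600 PrismRA and 1,500 control patients; Week 24 CDAI missing in up to 45% and 50%; success rates 40% and 30%; two-sided alpha 0.05.

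**Inputs assumed, because the documents give none.** Switch share *s* of 10% to 30%, and the ratio of missingness in switchers to that in non-switchers. I also assume that missingness is unrelated to response among non-switchers. I read the completion clause in SAP 3.1 as meaning no switch, as SAP 3.2 does.

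**Plan's own figure.** 600 × 0.55 = 330 and 1,500 × 0.50 = 750. Fisher's exact test by enumeration gives 88.4% power and a pooled z-test 89.1%, against the stated 88%. The figure is reproduced.

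**Formula.** Let *P* be the true composite rate, *m* overall missingness, and *mn* and *ms* missingness in non-switchers and switchers, with *m* = (1 − *s*) × *mn* + *s* × *ms*. All successes are non-switchers, so

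complete-CDAI rate = *P* × (1 − *mn*) / (1 − *m*).

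If *ms* = 1.5 × *mn*, then *mn* = *m* / (1 + 0.5*s*). At *s* = 20%:

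- PrismRA: *mn* = 0.45/1.10 = 0.409; rate = 0.40 × 0.591/0.55 = 43.0%.
- Control: *mn* = 0.50/1.10 = 0.455; rate = 0.30 × 0.545/0.50 = 32.7%.

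**Difference in points (true value 10).**

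| Pattern | s = 10% | s = 20% | s = 30% |
|---|---|---|---|
| Missingness unrelated to switching | 10.0 | 10.0 | 10.0 |
| Ratio 1.5 in both arms, same s | 10.1 | 10.2 | 10.4 |
| Ratio 1.5 in PrismRA only | 11.6 | 13.0 | 14.3 |
| Ratio 1.5 in controls only | 8.6 | 7.3 | 6.1 |

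In the one-arm rows the odds ratio moves from 1.56 to between 1.30 and 1.85. With ratio 1.5 in both arms but 10% switching in PrismRA and 20% in controls, the rates are 41.6% and 32.7%, a difference of 8.8.

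**Patients removed at s = 20%.** With missingness unrelated to switching: 600 × 0.20 × 0.45 = 54 and 1,500 × 0.20 × 0.50 = 150. At ratio 1.5: about 74 and 205. If the matched control set is twice the PrismRA arm (SAP 6.3), 1,200 × 0.20 × 0.50 = 120. These counts assume that every switch is documented.

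**Why simple pooling is not the repair.** Adding all switchers back while still dropping non-switchers without a CDAI over-weights failures. At *s* = 15% with missingness unrelated to switching:

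- PrismRA: 0.22 / (0.15 + 0.85 × 0.55) = 35.6%.
- Control: 0.15 / (0.15 + 0.85 × 0.50) = 26.1%.

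**Stratified version.** (1 − *s*) × observed non-switcher success rate gives 0.85 × (0.40/0.85) = 40% and 0.85 × (0.30/0.85) = 30%, whatever the ratio of missingness.

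**The case against.** **Only a supportive analysis is touched.** This stands. In the main analysis a recorded switcher fails whatever CDAI is imputed. SAP 5.4 also commits to describing missingness by arm and comparing patients with complete and incomplete outcomes. That description is not by switch status, however, so it does not repair the filter.

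**The size is unknown.** This stands too. A reader might infer that the result will move by several points, but dropping these patients is not enough for that. Switchers and non-switchers must differ in missingness, and the pattern or the switch share must differ between arms. For example, 15% switching with switchers missing 65% in PrismRA and 35% in controls gives 42.6% against 28.4%, or 14.2 points; the reverse gives 7.1. Nothing in the documents supports either split. Some difference between arms is plausible, since PrismRA has scheduled visits within 2 weeks and controls have routine encounters within 4 (Protocol 8.6).

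**Switch status may itself be unknown.** This qualifies the point. Neither document says how a switch is ascertained. PrismRA medication and adherence checks fall at Visits 3 and 4, the same visits that yield the CDAI (Protocol 8.6), and access to outside records depends on a release form (Protocol 8.2). Controls have linked claims (Protocol 6.2). Not every PrismRA switcher without a CDAI is therefore a known failure, and the stratified version is not immune. In the limiting case where no such PrismRA switch is seen (*s* = 15%, missingness unrelated to switching), the recorded share is 0.15 × 0.55 = 0.0825 and the estimate is (1 − 0.0825) × (0.40/0.85) = 43.2% instead of 40%. Simple pooling would give 40.0% against 26.1%, with true rates of 40% and 30%.

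**The Table 4 denominator.** The Table 2.1 note reads "Programmer note: N= number of patients with moderate or high disease activity; n= number of patients achieving endpoint criteria". A reader might infer that completers would be divided by everyone, printing 0.40 × 0.55 = 22% against 0.30 × 0.50 = 15%. The documents do not establish this: the shared layout fixes the columns, and 6.3.2 sets the population.

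**Conclusion.** The point holds as a defect in the definition of the sensitivity analysis. Read together, SAP 3.1, 6.3.2, 6.4.2 and the Table 4 title remove documented switchers without a CDAI, although their composite outcome is failure, and no other text restores them. A difference between Table 4 and Table 2.1 would mix this removal with the effect of the missing-data assumption.

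The size is conditional on the assumptions listed in the working: no shift if missingness is unrelated to switching, under 0.5 point if a ratio of 1.5 and the switch share are common to both arms, and about 1.4 to 4.3 points in either direction if that ratio applies in one arm only. Larger shifts need more extreme assumed patterns. It would be wrong to conclude that the primary result is biased or the study underpowered on this account.

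**What to change.** In SAP 6.3.2, 6.4.2 and Table 4, for the composite endpoints:

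- Count documented switchers by the visit as failures, with or without a CDAI.
- Apply the complete-CDAI restriction to non-switchers only.
- Combine the two groups by their full-cohort shares, i.e. (1 − switch share) × observed non-switcher success rate. Equivalently, weight observed non-switchers up to all non-switchers within each arm and multiply by the matching weight in the logistic model. Do not simply pool all switchers with the observed non-switchers.
- Report by arm the switch rate, Week 12 and Week 24 missingness by switch status, and how switch status was ascertained when the CDAI is missing. Show patients of unknown status separately rather than counting them silently as non-switchers.
- State the number analysed in Table 4.
- Keep the plain complete-CDAI filter for the Treatment Policy version, where it fits, and add a matching table.

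The cost is revised SAP wording, a derivation flag, simple weighting and one repeated table. No new data are needed.

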6.4 Analyses Addressing Secondary Study Endpoints

Secondary endpoints are outlined in Section 3.2.

6.4.1 Secondary Analysis

Statistical approaches for secondary study endpoints follow all methods described in Section 6.3.

For binary endpoints, the proportion of patients within each study arm meeting the outcome of interest will be calculated. Odds ratio and 95% CI will be estimated using weighted logistic regression.

For the continuous endpoint (change in CDAI scores), the average change in CDAI scores along with the average difference and 95% CI estimated using weighted least squares will be reported.

6.4.2 Sensitivity Analysis

Sensitivity analyses will assess the robustness of treatment effect estimates to limiting primary endpoints to patients who have the complete CDAI scores.

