For the primary efficacy analysis multiple imputation (MI) will be used with the assumption that patients with unreported outcome measures at 12 and 24 weeks have outcome events that are non-informative under the missing at random (MAR) assumption. This assumes that missingness occurs independent of the unobserved outcome: that is, the possibly unknown true outcome for a patient is the same regardless of whether it is actually observed. This assumption underlies the ITT principle, which analyses all eligible patients according to the treatment group to which they were assigned regardless of subsequent missingness.

For all approaches using MI, fully conditional specification (FCS) methods will be used, which assume the existence of a joint distribution for all variables. [10] All eligible patients meeting inclusion and exclusion criteria and initiating the study treatment will be used to impute missing observations. Imputation models will include all relevant available observations at baseline and 12 and 24 week follow up visits. Separate MI models will be used to create m imputed datasets for each study arm and combined into m analysis datasets with complete data. The choice of m will be determined by the fraction of missing information in the variables to be imputed. [11] MI performed separately within each study arm maintains the structure of the missing data patterns and the relationship between covariates specific to each database and ensures that no outcome information is used in PS matching. [12] Each imputation model will include all covariates listed in Table 4 of Section 6.2 along with the dependent variables and continuous scores for each study outcome as specified in Section 3.0. Dichotomous endpoints will be derived based on continuous scores within each imputed dataset. Analyses will proceed as described in Sections 6.3 and 6.4 using each of the imputed datasets. Finally, treatment effect estimates will be averaged using Rubin's rule [13] to obtain a pooled estimate with standard errors.

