6.3.1 Main Analysis

Main analyses will proceed according to the following order of procedures:

- 1) Perform single imputation for all missing pre-treatment covariates.
- 2) Estimate the probability of treatment with PrismRA for matching. Only pre-treatment covariates will be included as predictors of treatment (e.g., blinded to outcomes).
- 3) Perform stratified PS matching and describe patient characteristics of this single matched cohort. Matched external control arm should be weighted following the principle in Section 6.3 before describing patient characteristics.
- 4) Impute missing outcome data using MI as described in Section 5.4.
- 5) Within each imputed dataset, fit treatment effect outcome model with arm assignment as the independent variable with covariates adjustment.
- 6) Pool treatment effect estimates using Rubin's rule.

Steps 1-4 will be performed once at the start of analyses for each analysis population. Steps 5 and 6 will be repeated for each study endpoint and for the Treatment Policy Strategy and Composite Strategy.

Outcome regression models may also include direct adjustment for important patient covariates (e.g. age, sex, race/ethnicity, RDCI, baseline scores). In general, these methods improve confounding control in cases of imperfect matching and stratification. [30] The proportion of patients within each study arm with moderate or high disease activity at baseline who achieve an MID in CDAI of ≥ 6 (baseline moderate) or ≥ 12 (baseline high) at 24 weeks after study treatment initiation will be reported. Odds ratio and 95% CI will be estimated using weighted logistic regression.

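### The sensitivity analysis for secondary endpoints (SAP 6.4.2) filters on complete CDAI scores, so the PtGA, RAPID3 and pain rows of Table 4 would not test robustness to their own missing data

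*SAP*

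**What the plan says.** SAP 6.3.2 gives the sensitivity analysis for the primary endpoint as "limiting primary endpoint to patients who have the complete CDAI scores". SAP 6.4.2, under the heading for secondary endpoints, gives the same rule with one word made plural: "limiting primary endpoints to patients who have the complete CDAI scores". Neither section says which visits must have a CDAI score, and no other completeness rule is given for any secondary endpoint.

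The results go into "Table 4 Sensitivity analyses of primary and secondary composite strategy study endpoints for modified ITT cohort by study arm". The shell instruction is "The following Table will be created using the same layout as Table 2.1", and that layout contains rows such as "RAPID3 MCID at 24 weeks".

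The default for missing outcomes is multiple imputation of every outcome, not only CDAI. SAP 5.4 puts into each imputation model the "dependent variables and continuous scores for each study outcome as specified in Section 3.0". SAP 6.4.1 adds: "Statistical approaches for secondary study endpoints follow all methods described in Section 6.3". SAP 6.3.1 says that "Steps 5 and 6 will be repeated for each study endpoint", so each endpoint is analysed on the imputed datasets.

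**The concern.** A complete-case sensitivity analysis should show what happens when an endpoint's own imputed values are left out. A filter on CDAI does this for CDAI endpoints only. For RAPID3, pain and PtGA it selects patients on a different variable and leaves the default imputation in force for the variable being analysed.

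The SAP expects roughly 45% of the PrismRA arm and 50% of controls to lack Week 24 outcome data (SAP 5.4). This restriction is the only missing-data sensitivity analysis to which the plan commits. The censoring-weight and tipping-point analyses in SAP 8.0 are optional. A reader of Table 4 would take the PtGA, RAPID3 and pain rows as evidence that those results withstand their missing data, which the rows would not show.

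**Working it through.** **Rows affected.** The Table 2.1 layout has 12 rows:

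| Endpoint | Status in SAP 3.1–3.3 | Rows | Score behind it |
|---|---|---|---|
| CDAI MID, Week 24 | primary | 1 | CDAI |
| CDAI MID, Week 12 | secondary (c) | 1 | CDAI |
| LDA or remission, Weeks 12 and 24 | secondary (a) | 2 | CDAI |
| PtGA, Weeks 12 and 24 | secondary (d) | 2 | PtGA |
| RAPID3, Weeks 12 and 24 | secondary (e) | 2 | RAPID3 |
| Pain, Weeks 12 and 24 | secondary (f) | 2 | pain scale |
| ACR50, Weeks 12 and 24 | exploratory (a) | 2 | several components |

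Secondary rows: 1 + 2 + 2 + 2 + 2 = 9. Secondary rows not based on CDAI: 2 + 2 + 2 = 6. Endpoint (b), change in CDAI, is reported in the Table 3.1 layout and is not in Table 4.

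**Possible readings of 6.4.2.**
1. Filter on CDAI and keep the default methods. A CDAI-complete patient without RAPID3 stays in the RAPID3 row with an imputed value. A patient with RAPID3 but no CDAI is removed.
2. Filter on CDAI, then also drop patients whose own score is missing. The SAP does not state the second step, and patients with an observed score but no CDAI are still lost.
3. Take the words literally, so that only the primary endpoint is restricted. There is then no secondary sensitivity analysis, which contradicts the section's heading and the title of Table 4.

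None of the three gives a complete-case analysis of PtGA, RAPID3 or pain that uses all the observed data.

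**Where scores can be missing while CDAI is present.** Controls must have a baseline CDAI and joint counts (SAP Table 2, items 3, 4 and 8). No baseline PtGA, RAPID3 or pain score is required, although endpoints (d) to (f) are changes from baseline. Control data come from routine encounters without an enforced schedule (Protocol 8.6), and control CDAI may be estimated by machine learning from unstructured records (SAP 4.0). In the PrismRA arm, patient global, pain and RAPID3 are scheduled at Visits 1, 3 and 4, alongside the joint counts (Protocol 8.6). The mismatch could therefore differ between arms.

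**Size.** The plan's own attrition figures give the CDAI-complete numbers at Week 24: 600 × (1 − 0.45) = 330 and 1,500 × (1 − 0.50) = 750. With these, 40% versus 30% and a two-sided 0.05 Fisher test, exact enumeration gives 88.4% power, which reproduces the stated 88%. The documents give no figure for the share q of CDAI-complete patients who lack another score. For illustration only, with the same assumed q in both arms:

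| q | Imputed, PrismRA (330q) | Imputed, control (750q) | CDAI-complete with own score observed |
|---|---|---|---|
| 0% | 0 | 0 | 330 / 750 |
| 10% | 33 | 75 | 297 / 675 |
| 20% | 66 | 150 | 264 / 600 |
| 30% | 99 | 225 | 231 / 525 |

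The last column leaves out patients with the score but no CDAI, whom a correct rule would add back.

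**Visit.** If complete means a CDAI score at both visits, patients seen at Week 12 but not Week 24 drop out of the Week 12 rows, including the CDAI rows. If it means the visit of that row, they do not. The SAP does not say which.

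**The case against.** The strongest reply is that this is copied wording in a supportive table. The primary endpoint and its sensitivity analysis do not depend on it, and the study is not powered on the affected endpoints. All of that stands, and it limits the importance of the point.

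Four stronger inferences are tempting, and the documents do not support them.

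- **That a known, large share of these rows is imputed.** SAP 6.4.2 does not say what happens to a missing RAPID3, pain or PtGA value in this subset. Imputation follows from the default in 5.4 and 6.4.1, and only where such values are missing. The share could be zero.
- **That 8 of the 12 rows are wrong.** That count includes ACR50, which is exploratory, may be only descriptive in controls (SAP 3.3) and enters Table 4 only through the reused layout.
- **That PtGA is affected like the others.** Taking patient global to be a component of CDAI, which the SAP does not spell out, an investigator-assessed CDAI in the PrismRA arm implies an observed PtGA. The exposure is then mainly in controls with an estimated CDAI.
- **That Week 12 patients are certainly lost.** This depends on one reading of complete.

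The reply does not rescue the rule itself. The stated filter is the wrong one for six rows that the plan says it will report.

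**Conclusion.** The point holds as a wrongly specified rule. For 6 of the 9 secondary rows in Table 4, SAP 6.4.2 selects on CDAI when the endpoint rests on another score, so those rows would not test robustness to that score's missing data. The conclusion rests on Table 4 covering the secondary endpoints, as its title says, and on multiple imputation remaining the default because nothing switches it off. The number of imputed values cannot be derived from the documents; the table above is an illustration. The primary endpoint is unaffected. The Week 12 loss is an ambiguity to settle, not an established effect. The correction should be made before the analysis, but it does not bear on the study's main conclusion.

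**What to change.** Replace the sentence in SAP 6.4.2 with:

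*For each secondary endpoint and visit, the sensitivity analysis is limited to patients with an observed baseline value and an observed value at that visit of the score that defines that endpoint; no imputed outcome values are used. Patients with a post-baseline treatment switch, who are failures under the Composite Strategy, are handled in the same stated way in 6.3.2 and 6.4.2.*

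The SAP then has to state that handling. A switcher without a score is already a known failure under the Composite Strategy. Dropping such patients discards a known outcome. Keeping them while non-switchers without a score are dropped tilts the set towards failures. Either choice can be defended if it is fixed in advance and used in both sections.

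The Table 4 layout already shows n/N, so only N needs defining, as the set above for each row. Either remove the ACR50 rows from Table 4 or apply the same rule to all ACR50 components.

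The cost is a short SAP edit, a matching line in 6.3.2 and a programming note for Table 4. No new data are needed.
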